Randomization will be performed by the DCC and either corticosteroid or placebo therapy will be initiated within 72 hours after portoenterostomy; doses will be adjusted according to the dosing schedule outlined in Table 4. The dose and regimen for corticosteroids were based on prior uncontrolled clinical reports in infants with biliary atresia⁴⁶⁻⁴⁹. The choice of the corticosteroid prednisolone is consistent with these reports, and may represent an additional safety feature in view of the lower plasma and biological tissue half-life that is typical for prednisolone when compared to dexamethasone. The decrease in half life of prednisolone may decrease the cumulative exposure to high levels of glucocorticoid function, thus decreasing the potential risk of toxicity to subjects randomized to receive corticosteroids. Corticosteroids or placebo will be given intravenously for at least 2 post-operative days or until the infant resumes oral or enteral feedings. When the infant is tolerating oral or enteral feedings, prednisolone or placebo will be given orally for the remainder of the course of study drug/placebo. Compounding of placebo by a registered pharmacist (see below) will match the corticosteroid product for appearance and taste.

Table 4. Schedule and Dosing of Corticosteroids or Placebo Following Portoenterostomy in Infants with Biliary Atresia.

Day/week of dosing	Corticosteroids*	Placebo
Days 1-7		
days 1-3	Methylprednisolone, IV – 4 mg/kg/day, divided BID	IV – Normal saline (same volume, BID)
days 4-7	Prednisolone, PO – 4 mg/kg/day, divided BID	PO – Placebo (same volume, BID)
Week 2	4 mg/kg/day, divided BID	PO same volume BID
Week 3	2 mg/kg/day, divided BID	PO same volume BID
Week 4	2 mg/kg/day, divided BID	PO same volume BID
Week 5	1 mg/kg/day, once a day	PO once a day
Week 6	1 mg/kg/day, once a day	PO once a day
Week 7	0.8 mg/kg/day, once a day	PO once a day
Week 8	0.6 mg/kg/day, once a day	PO once a day
Week 9	0.4 mg/kg/day, once a day	PO once a day
Week 10	0.2 mg/kg/day, once a day	PO once a day
Week 11	0.1 mg/kg/day, once a day	PO once a day
Week 12-13	0.1 mg/kg/every other day	PO every other day
Week 14	Stop	Stop

*Initial dosage will be based on subject’s weight. Subsequent doses will be adjusted based on subject’s weight measured monthly at each scheduled outpatient visit.

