Infants who have received the live attenuated rotavirus vaccine (e.g. Rotateq) within 5 days prior to proposed administration of study drug are excluded from the study. Infants who have received the vaccine prior to this interval should not receive their first dose of steroids until a total of 5 days post vaccination has elapsed.

4.F2. Dose Reduction

In the event that a subject has a potential expected or unanticipated side effect of the study drug/placebo (such as irritability) but there is no indication to stop the study drug/placebo, the clinical site PI will have the option to reduce the dose of the study drug/placebo by 50%. The subject will then be monitored for improvement in these symptoms. If the symptoms improve within 48 hours, the subject will be maintained at the reduced dose for the remainder of the days planned for the original dose, as well as for the duration of treatment with this dose according to the normal taper schedule (Table 4). If symptoms do not improve/resolve, a further reduction by 50% of the new dose will be considered by the clinical site PI. Any reduction in the dosage of study drug/placebo will be reported to the DCC by the clinical site PI, along with the notification of the adverse event. If the symptoms persist beyond 48 hours and the clinical site PI judges it necessary that the study drug/placebo be discontinued, the tapering and discontinuation protocol outlined below will be followed.

4.F3. Tapering and Discontinuation of Study Drug or Placebo in the Event of a Serious Adverse Event (SAE) or Early Withdrawal

Blinded taper: If a SAE (see definition in Section 7.B3) is documented and thought by the clinical site PI to be possibly related to the study drug/placebo or if the subject withdraws from the study before the completion of the study drug/placebo, the clinical site PI will initiate a blinded taper of the study drug/placebo following the schedule outlined in Table 5 (below). The taper will be implemented in a blinded fashion in order to maintain objectivity in subject care and data collection during follow-up visits for the duration of the study.

Table 5. Tapering Protocol for Discontinuation of Study Drug or Placebo

Duration of treatment	Plan
Week 1	No need to taper; discontinue study drug or placebo
Weeks 2-8	Decrease dose to 0.6 mg/kg/day study drug/placebo orally x 7 days Then decrease the dose by 50% x 7 days and stop
Weeks 9-10	Decrease the dose by 50% for 7 days and stop

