6. HUMAN SUBJECTS RESEARCH CONSIDERATIONS

6.A. Risks to Study Subjects

6.A1. Involvement of Subjects

Subjects will be recruited into this study at the time that biliary atresia is suspected and exploratory surgery is scheduled or within 72 hours following portoenterostomy. Subjects will be randomized to treatment with corticosteroids or placebo treatment for 13 weeks and followed as outpatients until age 24 months.

6.A2. Planned Duration of the Entire Study

Based on the anticipated enrollment of 40-50 subjects/year by all ChiLDREN centers, we estimate completing enrollment within 3-4 years, with an additional 6 months to gather follow-up data on subjects enrolled in the final year. However, the testing of secondary outcome measures (such as survival with native liver at 24 months of age) and the careful monitoring of potential long-term adverse effects of corticosteroids (such as administration of developmental tests to screen for impaired neurodevelopmental outcome at 1 and 2 years of age) will extend the overall duration of the study to 6 years.

6.A3. Duration of Participation for Each Subject

Each subject will remain in the clinical trial until 24 months of age; i.e, for between 18 and 24 months. The use of corticosteroids will be limited to 13 weeks. This will be followed by very close follow-up in outpatient clinics until 12 months of age, followed by outpatient visits at 18 and 24 months of age. Subjects will be seen clinically as needed (by either their primary care provider or by a gastroenterologist at the study site) for evaluation and management of medical problems that may arise because of the natural progression of liver disease in affected children.

6.A4. Sources of Research Material

Subjects will be recruited from the pool of infants with jaundice referred to or evaluated by the outpatient and inpatient services at the ChiLDREN clinical centers. Research material will include clinical and laboratory data, physical findings, and data collected as part of the prospective observational database.

6.A5. Potential Risks to Subjects

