Because a single diagnostic test for pancreatitis is not available, a combination of tests and the best clinical judgment of the local PI will be used when evaluating the subject for possible pancreatitis. If there is new onset irritability presumed due to abdominal discomfort, progressive abdominal distension, inability to feed and/or vomiting, a serum lipase and/or pancreatic ultrasound will be ordered. If serum lipase is elevated (three times above the upper limit of normal) or ultrasound findings of pancreatitis are present⁸², this will be reported as a moderate AE; the clinical site PI will have the option to initiate study medication dose reduction (Section 4.F2). If the symptoms persist or require narcotic pain medication, or are associated with a pancreatic pseudocyst, hypocalcemia or anemia felt to be secondary to hemorrhagic pancreatitis, a SAE will be reported, and drug or placebo will be tapered and discontinued (Section 4.F3).

7.D7. Irritability

The development of severe irritability in the subject without an obvious cause will be considered a moderate AE, defined as the presence of inconsolable, persistent crying without an apparent cause, which requires evaluation and confirmation by the primary care provider or a visit to an emergency department if the subject is being followed as an outsubject, or by the clinical insubject team if the subject is in hospital at the time of the

event. Following evaluation for irritability and if no obvious cause is identified, a 50% dose reduction of study drug or placebo (Section 4.F2) will be considered by the clinical site PI. If the irritability resolves on this reduced dose, the duration of reduced dose will be the same as for the original dose, and the subject will continue to follow the remainder of the scheduled study drug/placebo regimen. The Medical Safety Officer will monitor all decreases in dose by clinical centers. If severe irritability persists despite the decrease in dosage, the study drug/placebo will be reduced by an additional 50%. If severe irritability persists despite this new reduction in dosage, the subject will undergo the tapering protocol and discontinuation of the study drug/placebo (Section 4.F3).

7.D8. Hypersensitivity Reaction to Trimethoprim-Sulfamethoxazole

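### Sections 4.F2 and 7.D7 conflict on how long a reduced dose lasts and what follows it, and neither says what follows a second reduction

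*Protocol*

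**What the plan says.** Section 4.F2 covers infants who have a possible side effect but no reason to stop study drug. There "the clinical site PI will have the option to reduce the dose of the study drug/placebo by 50" per cent. If symptoms improve within 48 hours, the infant is "maintained at the reduced dose for the remainder of the days planned for the original dose, as well as for the duration of treatment" that Table 4 gives to that dose. The reduced dose therefore has two periods: what is left of the original step, and the period Table 4 gives to the reduced dose. If symptoms do not improve, "a further reduction by 50% of the new dose will be considered by the clinical site PI"; no duration is given for that second step.

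Section 7.D7 deals with irritability, which is also the example named in 4.F2, and refers back to 4.F2. If irritability resolves after the first cut, "the duration of reduced dose will be the same as for the original dose, and the subject will continue to follow the remainder" (meaning what is left of Table 4). It says nothing about the Table 4 period of the reduced dose. If irritability persists, 7.D7 directs a second 50% cut, and if that fails, taper and discontinuation. Section 7.D1 (hypertension) also directs a second reduction, without a duration.

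Table 4 gives 4 mg/kg/day in weeks 1–2, "2 mg/kg/day, divided BID" in each of weeks 3 and 4, 1 in weeks 5–6, then 0.8, 0.6, 0.4, 0.2 and 0.1 in weeks 7 to 11, and 0.1 mg/kg every other day in weeks 12–13. Section 6.A3 adds: "The use of corticosteroids will be limited to 13 weeks".

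**The concern.** Two sections give different instructions for the same event, and the 4.F2 rule works cleanly only where half of a step is the next step in Table 4. Where it is not, a site has to choose. One available choice, rejoining Table 4, raises a dose that had been lowered because of a suspected side effect.

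Two things are at stake. One is safety: whether a reduced dose may rise again should be decided by the protocol, not by which sentence a site happens to read. The other is exposure: the dose received in the active arm after a reduction depends on that reading. Sections 7.D1, 7.D2, 7.D3, 7.D5, 7.D6 and 7.D7 all send sites to 4.F2, so its gaps reach well beyond irritability.

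**Working it through.** **Inputs.** Step doses and weeks from Table 4; a 50% reduction from 4.F2; the follow-on rules of 4.F2 and 7.D7. The protocol states no figure to reproduce. Doses are in mg/kg/day.

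**Single reduction.** Halved dose = step ÷ 2. Under 4.F2, find the Table 4 weeks that carry the halved dose. Under 7.D7, taking the duration as the remaining planned days, go to the next Table 4 step. Ratio = next step ÷ halved dose.

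| Step (weeks) | Halved | Table 4 weeks at halved dose | 4.F2 then gives | 7.D7 then gives | Ratio under 7.D7 |
|---|---|---|---|---|---|
| 4 (1–2) | 2 | 3–4 | 2 | 2 | 1.0 |
| 2 (3–4) | 1 | 5–6 | 1 | 1 | 1.0 |
| 1 (5–6) | 0.5 | none | undefined | 0.8 (week 7) | 0.8/0.5 = 1.6 |
| 0.8 (7) | 0.4 | 9 | 0.4 (week 8) | 0.6 (week 8) | 0.6/0.4 = 1.5 |
| 0.6 (8) | 0.3 | none | undefined | 0.4 (week 9) | 0.4/0.3 = 1.33 |
| 0.4 (9) | 0.2 | 10 | 0.2 | 0.2 | 1.0 |
| 0.2 (10) | 0.1 | 11 | 0.1 | 0.1 | 1.0 |
| 0.1 (11) | 0.05 | 12–13, as an average | 0.05 | 0.05 | 1.0 |

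In the 0.8 row, 4.F2 names the rest of week 7 and the week-9 period but not week 8. The entry 0.4 assumes that being maintained means no interruption.

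**Cumulative size.** The full Table 4 course is 14×4 + 14×2 + 14×1 + 7×(0.8 + 0.6 + 0.4 + 0.2 + 0.1) + 7×0.1 = 56 + 28 + 14 + 14.7 + 0.7 = 113.4 mg/kg (nominal mg; weeks 12–13 counted as seven doses). Compare rejoining Table 4 with holding the halved dose until Table 4 is no higher:
- From 0.8: (0.6 − 0.4)×7 = 1.4 mg/kg.
- From 1: (0.8 − 0.5)×7 + (0.6 − 0.5)×7 = 2.8 mg/kg.
- From 0.6: (0.4 − 0.3)×7 = 0.7 mg/kg.

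The largest is 2.8/113.4, about 2.5% of the course. For the cuts from 1 and 0.6, holding is itself an assumption, since 4.F2 gives no period.

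**If 7.D7 restarts a full period.** Take a cut from 4 to 2 after 7 of the 14 days, then a fresh 14 days at 2, then weeks 3–13 (77 days) in full: 7 + 14 + 77 = 98 days, against 13×7 = 91. The dose still does not rise, but agreement with 4.F2 is lost and the 13-week limit in 6.A3 is passed.

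**Second reduction.** No section gives a duration or follow-on dose. The quarter doses from 2, 1 and 0.6 (0.5, 0.25, 0.15) are not in Table 4. To show how much the silence leaves open, take cuts to 2 on day 4 and to 1 on day 6. Through day 14 the infant receives 3×4 + 2×2 + 9×1 = 25 mg/kg. Then:
- Rejoin Table 4 in week 3: 25 + 28 + 14 + 15.4 = 82.4 mg/kg, with 2 given again in weeks 3–4.
- Hold 1 until Table 4 reaches it: 25 + 14 + 14 + 15.4 = 68.4.
- Give 1 for its two-week period, then move on: 25 + 14 + 15.4 = 54.4, ending two weeks early.

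Each path fills a gap. None is prescribed.

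**The case against.** A reader might infer that the protocol returns infants to the very dose at which a side effect persisted. The documents do not support that. It needs a second reduction. 4.F2 says nothing about what follows one, and the 7.D7 sentence on duration applies when irritability resolves after the first cut. After the second cut, 7.D7 says only what to do if irritability persists. The path 4 to 2 to 1 and back to 2 is possible if a site simply rejoins Table 4; it is not ordered.

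Nor does the rule generally push doses up. A single cut from 4 or 2, in the high-dose weeks 1–4, never leads to a higher dose, and where a rise does follow a single cut the new dose (0.8, 0.6 or 0.4) is below the one at which the cut was made (1, 0.8 or 0.6). Holding 0.4 from week 7 through week 9, the natural sense of 4.F2, gives no rise.

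It would also be too strong to call any rise unsupervised. Side effects are reviewed at every scheduled visit, reductions are reported to the DCC, and 7.D7 has the Medical Safety Officer monitor them. All of this stands. Still, no check is tied to a rise, and visits fall at 2 weeks and at 1, 2 and 3 months, so a rise at the start of week 7 comes between visits.

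Finally, reduction is at the site's option and the analysis is intent-to-treat, so some variation in exposure is built in and the randomised comparison remains valid. That limits the statistical weight of the point but does not resolve conflicting instructions.

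**Conclusion.** The conflict is real but narrow. Of the eight Table 4 dose levels, five give the same follow-on dose under both sections after one cut, provided 7.D7 means the remaining planned days. At 0.8 the sections differ in week 8 (0.4 or 0.6), assuming 4.F2 means an unbroken hold. At 1 and 0.6 the halved dose has no place in Table 4: 4.F2 is undefined, and 7.D7 leads to a next dose 1.6 or 1.33 times the reduced one. In cumulative terms these single-cut differences are small, 0.7 to 2.8 mg/kg out of 113.4; what matters is that a reduced dose rises under one section and not under the other, or under no stated rule.

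The wider gap is the second reduction, which 7.D1 and 7.D7 direct but nobody defines. The 54.4 to 82.4 mg/kg range describes one constructed case, and the documents do not say how often two cuts would occur. The point is worth correcting because it concerns dosing instructions for infants after surgery. It does not threaten the primary analysis.

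**What to change.** Reconcile 4.F2, 7.D1, 7.D7 and Table 4 into one rule. The investigators should set out, for each Table 4 step, what follows one reduction and what follows two, for example in two added columns. They should also state:
- whether the reduced dose lasts for the remaining planned days or for a full new period;
- whether the dose may rise again after a reduction;
- whether the second reduction is optional or directed;
- whether the course still ends at 13 weeks.

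The doses and the rule are theirs to choose; none is proposed here. The cost is a protocol clarification, two table columns and an update of the site pharmacy instructions, with no extra infants, visits or procedures.

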The Medical Safety Officer will submit an expedited report to the FDA of an SAE when the SAE is unexpected and may be related (even remotely) to the study drug.

7.D. Monitoring and Management for Specific AEs

Several side effects of corticosteroids are anticipated in the subjects randomized to corticosteroid treatment. The following section outlines the plan for monitoring and management of these AEs. This monitoring will be conducted after portoenterostomy however before the first dose of study medication is given (to provide baseline data) and then at hospital discharge and at each scheduled follow up visit.

7.D1. Hypertension:

If a significant hypertension (systolic blood pressure ≥ 112 mmHg for infants <12 months of age)^{80a,b,c} is measured at least two times, and the subject is asymptomatic, a repeat blood pressure will be obtained within 24-48 hours. If the elevated blood pressure is resolved, no intervention will be necessary. If the repeat systolic blood pressure is ≥ 112 mmHg and the subject is asymptomatic, the study medication dose-reduction protocol (Section 4.F2) will be followed and a repeat blood pressure will be obtained within 48 hours; a mild AE will be reported⁷⁷. If the repeat systolic blood pressure remains ≥ 112 mmHg but the subject remains asymptomatic, anti-hypertensive monotherapy will be initiated (see below). If the hypertension persists beyond 48 hours, a second dose-reduction will be initiated and a second anti-hypertensive medication may be used (see below). If hypertension does not resolve within 48 hours or if the subject develops symptoms due to hypertension (e.g.: severe irritability, seizure) or as other life-threatening consequences, such as end-organ damage, drug or placebo will be tapered and discontinued (Section 4.F3), the subject will be referred to an emergency department, and additional anti-hypertensive treatment will be initiated. This will be reported as a SAE.

- a. Treatment choices for hypertension with BP ≥ 112 mmHg without symptoms
- Hydrochlorothiazide: 2 mg/kg/day given once or twice a day, or
 - Amlodipine: 0.2-0.4 mg/kg/day given once or twice a day, or
 - Captopril: 0.3-1 mg/kg/day given twice a day
 - Other site-specific treatment choice

b. Treatment choices for hypertension with BP \geq 112 mmHg with symptoms

- Nifedipine 0.25-0.5 mg/kg/ sublingual
- Labetolol: 1-3 mg/kg/hour IV
- Other site-specific treatment of choice

7.D2. Hyperglycemia

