A random plasma glucose level will be obtained at the time of discharge and at follow-up visits (Table 6). If the random plasma glucose level is 200 mg/dL or higher the study subject will return within 24 hours for a repeat level. If the repeat glucose level is 200 mg/dL or higher⁸¹, a moderate AE will be reported and the study medication dose-reduction protocol (Section 4.F2) will be followed if the subject is asymptomatic. Persistent hyperglycemia above 200 mg/dL beyond 48 hours of dose reduction and associated with acidosis or change in mental status due to elevated serum osmolality will be considered a SAE, and the drug or placebo will be tapered and discontinued (Section 4.F3). If blood glucose is 150-200 mg/dL, treatment or observation will be directed by the local standard of care, including the option for study medication dose reduction (Section 4.F2).

7.D3. Hypokalemia

A random serum potassium level will be obtained at the time of hospital discharge and at follow-up visits (Table 6). If the potassium level is less than the lower limit of normal but above 3.0 mmol/L, a mild AE will be reported. A new serum K level will be obtained in 48 hours. If the potassium level is less than 3 mmol/L but \geq 2.5 mmol/L, a moderate AE will be reported and appropriate replacement therapy will be initiated. Repeat serum potassium levels will be obtained at 24 and 48 hours after start of replacement. If the levels do not normalize and the subject is asymptomatic, increased replacement will be initiated and the subject will be monitored closely. The clinical site PI will have the option to initiate study medication dose reduction (Section 4.F2). If the potassium is less than 2.5 mmol/L, a SAE will be reported, replacement therapy will be given immediately, and the study drug or placebo will be tapered and discontinued (Section 4.F3), unless another cause is identified as the cause for the hypokalemia (such as use of furosemide or another diuretic that may be used because of progression of liver disease and development of ascites).

7.D4. Impaired Wound Healing

Impaired wound healing is defined as a situation in which any of the following conditions are met:

- Readmission due to wound healing complications after discharge following portoenterostomy,
- Delay in discharge due to wound healing complications after portoenterostomy,
- Wound infection after portoenterostomy that requires specific treatment with antibiotics

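### Two dosing lines do not fit all the infants they cover: ranitidine 12.5 mg BID leaves the protocol's own 2-6 mg/kg/day range below 4.17 kg, and Table 5's weeks 2-8 taper dose cannot be followed as a decrease by an infant already cut to 0.15-0.5 mg/kg/day

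*Protocol*

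**What the plan says.** **Ranitidine.** Sections 4.G and 4.M7 state a fixed oral dose of 12.5 mg twice daily, with 2-6 mg/kg/day in parentheses, for as long as study drug or placebo is given. Section 4.M7 applies it to all study subjects. The weight criterion in 4.C is 2000 g or more.

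**Taper.** Section 4.F2 lets the site investigator halve the study drug dose for a suspected side effect. If symptoms do not improve, "a further reduction by 50% of the new dose will be considered by the clinical site PI". If they persist and stopping is judged necessary, the infant goes to the taper in 4.F3, Table 5. The weeks 2-8 row there begins "Decrease dose to 0.6 mg/kg/day study drug/placebo orally x 7 days", followed by a further halving for 7 days and then stop. The weeks 9-10 row is relative: "Decrease the dose by 50% for 7 days and stop".

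Section 7.D sends dose-reduced infants to the same taper:
- 7.D7 (irritability), after two cuts: "If severe irritability persists despite this new reduction in dosage, the subject will undergo the tapering protocol and discontinuation".
- 7.D1 (hypertension), after two cuts: "If the hypertension persists beyond 48 hours, a second dose-reduction will be initiated and a second anti-hypertensive medication may be used", with the taper if blood pressure still does not settle.
- 7.D2 (hyperglycemia), after one cut: the trigger is "Persistent hyperglycemia above 200 mg/dL beyond 48 hours of dose reduction and associated with acidosis or change in mental status".
- 7.D3, 7.D5 and 7.D6 allow an optional cut before an SAE-driven taper.

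**The concern.** Each line pairs a fixed number with a rule that the number breaks for some eligible infants.

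For ranitidine, the fixed dose and the mg/kg range cannot both be met in a small infant, and 4.M7 makes the fixed dose apply to everyone. A pharmacist following it would exceed the upper end of the range printed beside it.

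For the taper, the row names an absolute dose with no provision for an infant already on less. Many of these infants are being stopped for suspected steroid toxicity. The word and the number then disagree, and a site could hold, halve or raise the dose. What is at stake is consistent and safe dosing of a few infants, not the trial's inference.

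**Working it through.** **Ranitidine.** Daily dose = 2 x 12.5 = 25 mg. Weight at the upper end of the range = 25/6 = 4.17 kg; at the lower end = 25/2 = 12.5 kg. The fixed dose is within 2-6 mg/kg/day only between these weights.

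| Weight (kg) | 25 mg/day as mg/kg/day | Dose at 6 mg/kg/day |
|---|---|---|
| 2 | 12.5 | 6 mg BID |
| 3 | 8.3 | 9 mg BID |
| 4 | 6.25 | 12 mg BID |
| 4.17 | 6.0 | 12.5 mg BID |

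**Taper.** Take the Table 4 dose for each step, halve it once or twice as in 4.F2, and divide 0.6 by the result. A ratio above 1 means the Table 5 number is higher than the current dose.

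| Table 4 step | Scheduled (mg/kg/day) | One cut | 0.6/dose | Two cuts | 0.6/dose |
|---|---|---|---|---|---|
| Week 2 | 4 | 2 | 0.3 | 1 | 0.6 |
| Weeks 3-4 | 2 | 1 | 0.6 | 0.5 | 1.2 |
| Weeks 5-6 | 1 | 0.5 | 1.2 | 0.25 | 2.4 |
| Week 7 | 0.8 | 0.4 | 1.5 | 0.2 | 3.0 |
| Week 8 | 0.6 | 0.3 | 2.0 | 0.15 | 4.0 |

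From 0.25 or less, the second taper step (0.3) is also above the current dose. The weeks 9-10 row halves whatever is being given, so it cannot have this problem.

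**When it arises.** The conflict needs the cut to be in force when the taper starts. The protocol describes how long a cut lasts in two places. Section 7.D7 says "the duration of reduced dose will be the same as for the original dose", after which the normal schedule resumes. Section 4.F2 adds the time for which Table 4 itself schedules that dose, so 2 cut to 1 in weeks 3-4 could run on as 1 through weeks 5-6. The weeks attached to a given dose therefore depend on the reading. Doses of 0.15-0.5 are reachable on either, because both duration clauses concern symptoms that improve; when symptoms persist, cut and taper can follow directly.

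**Timing of two cuts.** With a 48-hour wait after each cut, two cuts take 2 + 2 = 4 days. By 7.D1 the sequence is cut, recheck within 48 hours, monotherapy, 48 hours, second cut, 48 hours, taper: about 2 + 2 + 2 = 6 days. The 3x and 4x rows need both cuts within one 7-day step, so the first must fall in about the first 3 days (4-day sequence) or the first day (hypertension). They are corner cases.

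**Size if a site took the number literally.** Table 5 totals 0.6 x 7 + 0.3 x 7 = 6.3 mg/kg. A taper capped at current dose d totals d x 7 + (d/2) x 7 = 10.5d: 5.25 mg/kg from 0.5 and 1.58 from 0.15. The difference is 1.05 to 4.73 mg/kg. The full Table 4 course is 56 + 28 + 14 + 5.6 + 4.2 + 2.8 + 1.4 + 0.7 + 0.7 = 113.4 mg/kg, so this is about 1% to 4% of it.

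**Adrenal cover under a cap.** Table 3 equates 5 mg prednisolone with 20 mg hydrocortisone, a factor of 4. Body size is not in the protocol, so I assume 3 kg/50 cm, 4 kg/54 cm and 5 kg/58 cm (Mosteller area 0.204, 0.245 and 0.284 m2). Hydrocortisone equivalent = dose x 4 x weight/area, in mg/m2/day, for the first taper week:
- 0.5: 29-35
- 0.4: 24-28
- 0.3: 18-21
- 0.25: 15-18
- 0.2: 12-14
- 0.15: 9-11

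The physiologic replacement range in 4.F3 is 20-25. Cover is borderline at 0.3 and below the range at 0.25 or less.

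**The case against.** A reader might infer that Table 5 orders a steroid increase for infants with suspected toxicity. It does not: the row says to decrease, in a table about tapering, and no text authorises raising the dose. The excess computed above would occur only if a site acted against that verb. Safeguards also exist: reductions are reported to the coordinating center under 4.F2, and "The Medical Safety Officer will monitor all decreases in dose by clinical centers". This stands, and it reduces the point to a row that gives no usable dose.

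A reader might also take the step from 0.5 to 0.6 as the typical event. Nothing in the protocol says how often any of these situations occurs.

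The strongest clinical objection is that 0.6 may be deliberate. Sections 4.F3 and 7.F offer the weeks 2-8 doses of Table 5 as prednisolone replacement, and 6.A5b says the taper is there to guard against adrenal insufficiency. That is a fair reading, and it makes a cap at the lowest doses a clinical choice and not a matter of arithmetic. It does not rescue the present wording, because a floor cannot be described as a decrease for an infant who is below it.

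On ranitidine, a prescriber could let the printed range govern, infants should gain weight over 13 weeks, and the protocol never calls 6 mg/kg/day a safety limit. So harm cannot be inferred. The two printed instructions still conflict below 4.17 kg, and 4.M7 states the fixed dose for all subjects.

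**Conclusion.** Both points hold as minor dosing-safety corrections.

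- Ranitidine: the fixed dose contradicts the protocol's own range for any infant under 4.17 kg, reaching about twice the upper end (12.5 against 6 mg/kg/day) at the 2 kg eligibility limit. How many infants this covers is not stated.
- Table 5, weeks 2-8: the row cannot be carried out as a decrease for an infant on 0.15-0.5 mg/kg/day. Its number is 1.2 to 4 times the current dose, with the top ratios confined to corner cases. Week 2 is unaffected, as is one cut from the weeks 3-4 dose. An uncut infant in week 8 is already at 0.6.

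The weeks depend on how the 4.F2 duration clause is read, and the frequency is unknown. The arithmetic uses only Tables 4 and 5 and the stated cuts and weights. Only the adrenal-cover figures rest on assumed body sizes.

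**What to change.** **Ranitidine (4.G and 4.M7).** Dose by weight within 2-6 mg/kg/day, up to 12.5 mg BID, using the liquid under 4.17 kg: at most 6 mg BID at 2 kg and 9 mg BID at 3 kg. The cost is a weight calculation when each monthly supply is dispensed. Sections 4.M7 and 6.C2 already provide for the liquid.

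**Table 5, weeks 2-8.** Replace the row with: *Give the lower of the current dose and 0.6 mg/kg/day x 7 days, then decrease by 50% x 7 days and stop.* This keeps the 14-day taper and never raises the dose. The trade-off is less steroid cover for the most reduced infants, so the clinical team should confirm cover at 0.3 mg/kg/day or less. If they intend 0.6 as a replacement floor, the row should say that and drop the word for a decrease. It would also help to state in 4.F2 whether a cut carries over into the next Table 4 step.

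The whole change is a line or two in each place plus the pharmacy instructions, with no effect on sample size, blinding, data or analysis.

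### Table 5's fixed 0.6 mg/kg/day taper step raises the dose of some infants already on a reduced dose: 1.2- to 2-fold in weeks 5-8 after one reduction, 1.2- to 4-fold in weeks 3-8 after two

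*Protocol*

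**What the plan says.** Table 4 (Section 4.F1) schedules, in mg/kg/day, 4 in week 2, 2 in weeks 3-4, 1 in weeks 5-6, then "0.8 mg/kg/day, once a day" in week 7 and 0.6 in week 8.

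Section 4.F2 lets the site PI halve the dose for a suspected side effect. If symptoms do not improve, "a further reduction by 50% of the new dose will be considered by the clinical site PI". If they persist beyond 48 hours and the PI judges that study drug must stop, "the tapering and discontinuation protocol outlined below will be followed".

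Three event-specific sections lead to the same place:

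- **7.D1, hypertension.** After a first reduction and one antihypertensive, "a second dose-reduction will be initiated and a second anti-hypertensive medication may be used". If that fails within 48 hours, or symptoms appear, "drug or placebo will be tapered and discontinued (Section 4.F3), the subject will be referred to an emergency department".
- **7.D7, irritability.** After two reductions: "If severe irritability persists despite this new reduction in dosage, the subject will undergo the tapering protocol".
- **7.D2, hyperglycemia.** "Persistent hyperglycemia above 200 mg/dL beyond 48 hours of dose reduction", together with acidosis or a change in mental status, leads to the 4.F3 taper. This section names one reduction only.

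The blinded taper in 4.F3 is Table 5, whose rows are set by duration of treatment. For weeks 2-8 the instruction is "Decrease dose to 0.6 mg/kg/day study drug/placebo orally x 7 days", followed by a 50% cut for a further 7 days and then a stop. The weeks 9-10 row is relative: half of the current dose for 7 days, then stop. In weeks 11-13 the drug stops without a taper.

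**The concern.** An absolute first step works only if every infant reaching the row takes at least 0.6 mg/kg/day. The protocol's own reduction rules break that condition. An infant on the scheduled 1 mg/kg/day in weeks 5-6 is at 0.5 after one reduction and 0.25 after two, and the row then orders 0.6.

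These are infants whose study drug is being stopped because a suspected corticosteroid effect persisted after the dose was cut. Followed literally, the taper gives those in the active arm more prednisolone per day than the dose judged to need stopping, for the first week and in some cases for both weeks. If the row is instead read as never raising a dose, Table 5 has no row for them. What is at stake is dosing safety in a few infants. No endpoint, sample size or analysis depends on it.

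**Working it through.** **Inputs.** Scheduled doses from Table 4; each reduction multiplies the dose by 0.5 (Section 4.F2); taper steps of 0.6 and then 0.3 mg/kg/day, 7 days each, from Table 5.

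**Unreduced infants first.** The ratio 0.6 / scheduled dose is 0.15 in week 2, 0.30 in weeks 3-4, 0.60 in weeks 5-6, 0.75 in week 7 and 1.00 in week 8. The row never raises the dose of an unreduced infant.

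**Reduced infants.** Current dose = scheduled dose × 0.5 (one reduction) or × 0.25 (two). Ratio = 0.6 / current dose.

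| Week | Scheduled | After one | Ratio | After two | Ratio | Second step 0.3 / dose after two |
|---|---|---|---|---|---|---|
| 2 | 4 | 2 | 0.30 | 1 | 0.60 | 0.30 |
| 3-4 | 2 | 1 | 0.60 | 0.5 | **1.2** | 0.60 |
| 5-6 | 1 | 0.5 | **1.2** | 0.25 | **2.4** | **1.2** |
| 7 | 0.8 | 0.4 | **1.5** | 0.2 | **3.0** | **1.5** |
| 8 | 0.6 | 0.3 | **2.0** | 0.15 | **4.0** | **2.0** |

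So the first step is an increase in 4 of the row's 7 weeks after one reduction and in 6 of 7 after two: 10 of the 14 week-by-reduction combinations. After one reduction the second step never exceeds the current dose (at most 0.3 / 0.3 = 1.0, in week 8).

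**Totals over 14 days.** The taper gives 0.6 × 7 + 0.3 × 7 = 6.3 mg/kg. Staying on the current dose would give 14 × current dose:

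- 0.5 mg/kg/day: 7.0 mg/kg. The taper total is lower; the excess is 0.1 mg/kg/day in the first week only.
- 0.4 mg/kg/day: 5.6 mg/kg; 0.3 mg/kg/day: 4.2 mg/kg. The taper total is higher.
- 0.25, 0.2 and 0.15 mg/kg/day: 3.5, 2.8 and 2.1 mg/kg. The taper total is higher (for 0.25, 6.3 / 3.5 = 1.8 times), and both steps exceed the current dose.

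**Comparison within Table 5.** An unreduced infant stopping in week 9 (0.4 mg/kg/day) receives 0.2 × 7 = 1.4 mg/kg; in week 10 (0.2 mg/kg/day), 0.1 × 7 = 0.7 mg/kg. An infant on 0.15 in week 8 would receive 6.3 mg/kg, which is 6.3 / 1.4 = 4.5 times the week 9 total.

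**Do the routes fit the schedule?** Counting 48 hours per step, two failed reductions take about 4 days under 4.F2 or 7.D7 and about 6 days under 7.D1. Weeks 3-4 and weeks 5-6 are 14-day blocks at one dose, so both chains fit. Weeks 7 and 8 are single-week levels, so 3-fold and 4-fold require both reductions to start and fail inside that week.

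**The case against.** The strongest defence is that the row says to decrease, so no site would raise a dose under it, and that the natural step for an infant below 0.6 mg/kg/day (halve for 7 days and stop) already stands in the row's second clause and in the next row. A sensible site may well do that. But nothing in the protocol says to skip the first step, and on this reading the infant has no stated taper, although Section 6.A5b warns of adrenal insufficiency after sudden withdrawal.

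A second defence is that 0.6 mg/kg/day is a deliberate replacement floor: the unblinded taper in 4.F3, and 7.F, use the same doses as an oral replacement option. That use is legitimate and should stay. It does not explain the blinded row, which is worded as a decrease, and Table 5 applies no such floor from week 9 on.

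Three limits stand:

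- The dose is bounded. 0.6 never exceeds the scheduled, unreduced dose for the week in which the taper starts.
- The larger ratios are edge cases. By the 7.D1 route, 4-fold needs the first reduction at the very start of week 8. 7.D2 alone reaches at most 2-fold unless the optional second reduction of 4.F2 is used.
- The reduction must still be in force when the taper starts. An infant who has returned to the Table 4 schedule is not affected.

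A reader might infer that every infant with a prior reduction is escalated, or always receives more drug in total. The figures do not support either: 4 of the 14 combinations are true decreases, and at 0.5 mg/kg/day the 14-day total falls.

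**Conclusion.** The point holds for infants who are below 0.6 mg/kg/day when a blinded taper starts in weeks 2-8. For them the instruction cannot be followed as a decrease. The clearest case is two reductions in weeks 5-6: 0.25 mg/kg/day becomes 0.6 (2.4-fold), the second step is still 1.2-fold, and the two-week total is 1.8 times that of no change.

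The table assumes that the reductions occur at the dose level of the week shown and are in force when the taper begins. Doses are nominal in the placebo arm; only active-arm infants receive more prednisolone. The documents give no rate of dose reduction or of failed reduction, so no number of affected infants can be claimed, and it may be zero. The correction is minor but worth making, because it concerns infants being withdrawn for a persistent suspected steroid effect. It would be wrong to infer any effect on the primary result or on the analysis.

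**What to change.** Add a footnote to the weeks 2-8 row of Table 5, for the blinded taper only: *Give 0.6 mg/kg/day or the current dose, whichever is lower, for 7 days, then half of that dose for 7 days, then stop.* State that the oral replacement option of the unblinded taper (4.F3, 7.F) keeps 0.6 and then 0.3 mg/kg/day.

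Infants at or above 0.6 mg/kg/day are unaffected, including the unreduced infant in week 8. For those below, the 14-day total becomes 7 × dose + 7 × dose / 2 = 10.5 × dose: 5.25 mg/kg from 0.5, 4.2 from 0.4, 3.15 from 0.3, 2.63 from 0.25, 2.1 from 0.2 and 1.58 from 0.15. These totals are lower than the present 6.3 mg/kg, which is the price of the change, but all stay above the 1.4 and 0.7 mg/kg that Table 5 gives from weeks 9 and 10.

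The cost is one footnote and one line in the pharmacy instructions. The site pharmacist must know the current reduced dose; 4.F2 already requires each reduction to be reported to the DCC. Sample size, endpoints, blinding and analysis do not change.
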